#### **9.6.5 Physical Measurements**

The analyses of physical measurements will include summary statistics at all time points by treatment group.

#### **9.6.6 Electrocardiogram**

The ECG measurements will be performed as per standard of care for routine safety monitoring, rather than for purposes of assessment of potential QTc effect. Since these evaluations may not necessarily be performed under the rigorous conditions expected to lead to meaningful evaluation of QTc data, summaries and statistical analyses of ECG

measurements are not planned, and these data would not be expected to be useful for meta-analysis with data from other trials.

#### **9.6.7 Antibody Formation**

The incidence and percentage of subjects who develop anti-AMG 592 antibodies and cross-reactive anti-IL-2 antibodies (binding and if positive, neutralizing) will be summarized by treatment group. Furthermore, the incidence and percentage of subjects with treatment-boosted anti-AMG 592 antibodies will also be summarized. In addition, subjects with positive binding and neutralizing anti-AMG 592 results will be listed individually with corresponding time points.

#### **9.6.8 Exposure to Investigational Product**

Descriptive statistics will be produced to describe the exposure to investigational product by treatment group. The number of days on investigational product and the total dose of investigational product will be summarized using descriptive statistics. Subject-level data may be provided instead of the summary if the subject incidence is low or single dose is given.

Descriptive statistics of the total dose, **number of doses received**, duration of usage, **and** number and percentage of subjects with **number of doses received**, dose change/withheld and reasons for dose change/withheld will be summarized. **Number and percentage of subjects with** missed IP doses due to COVID-19 will be also summarized.

A listing of the unique manufacturing lot numbers and a listing of the subjects administered by each manufacturing lot number will be provided.

#### **9.6.9 Exposure to Concomitant Medication**

Number and proportion of subjects receiving therapies of interest will be summarized by preferred term or category for each treatment group as coded by the World Health Organization Drug dictionary.

### **9.7 Other Analyses**

Secondary endpoints in study include PK endpoints and immunogenicity endpoints. Exploratory endpoints in this study include biomarker endpoints, efficacy endpoint and PD endpoints.

### **9.7.1 Analyses of Pharmacokinetic or Pharmacokinetic/Pharmacodynamic Endpoints**

#### **9.7.1.1 Analysis of Pharmacokinetic Endpoint**

The Pharmacokinetic Concentration Analysis Set defined in Section 6 will be used in analyzing PK concentration data and the Pharmacokinetic Parameter Analysis Set will be used in analyzing PK parameters. Serum concentrations of AMG592 will be expressed in ng/mL. All concentrations below the limit of quantification or missing data will be labeled as such in the concentration data listings. Concentrations below the lower limit of quantification will be treated as zero in summary statistics.

Nominal sampling times will be used for individual concentration-time plots and tables. Actual dose administered, and actual sampling times will be used for the calculation of PK parameters for each subject. The reasons for excluding any sample from the analyses will be provided.

From the serum concentration-time data, the following PK parameters will be determined, as data permit: maximum observed concentration (Cmax), the time of maximum observed concentration (Tmax), and area under the concentration-time curve over a dosing interval (AUCtau) after the first and last doses.

Individual concentration-time data will be tabulated and presented graphically. Summary of PK concentration over time and PK parameters will be provided. Mean concentration time profiles for each dose will be provided. PK parameters will be summarized for each dose using descriptive statistics, including, but not limited to mean, standard deviation, CV, median and range by treatment group. Analyses will be conducted by Amgen Clinical Pharmacology Modeling and Simulation (CPMS).

#### **9.7.1.2 Analysis of Pharmacodynamic Endpoints**

The pharmacodynamic analysis set defined in Section 6 will be used. PD assessments include but are not limited to:

- Regulatory T cells (Treg), Conventional T cells (Tcon), CD8 T cells and Natural Killer (NK) absolute cell counts and percentages
- Treg/Tcon ratio

Fold changes from baseline in the above PD assessments at all time points will be summarized by treatment group. Furthermore, the mean (+/- standard error) of fold changes from baseline will be plotted for each treatment group at all time points. Due to the skewed distribution of PD data, the mean, standard deviation and standard error will

---

be estimated based on log-transformed data, and the estimates will be back-transformed and presented, which are equivalent to the geometric mean, geometric standard deviation and geometric standard error respectively.

To maintain the integrity of PD results, data collected at an early termination visit which is completed outside the protocol defined window (> 9 days after the last dose date for QW cohorts and > 16 days for Q2W cohorts) will not be included in the analysis. In addition, data collected at a visit after skipping one or more consecutive doses prior to the visit will be also excluded.

#### **9.7.2            Analyses of Biomarker Endpoints**

Absolute and change from baseline in anti-double stranded DNA (anti-dsDNA), and C3 and C4 complements at all time points will be summarized by treatment group.

#### **10.            Changes From Protocol-specified Analyses**

There are no changes to the protocol-specified analyses.

---

## 12. Appendices

### **Appendix A. Concomitant Medications/Adverse Event Missing Value Imputation Imputation Rules for Partial or Missing Stop Dates**

If the month and year are present, impute the last day of the month. If only the year is present, impute December 31 of that year. If the stop date is entirely missing, assume the event or medication is ongoing. If a partial or complete stop date is present and the 'ongoing' or 'continuing' box is checked, then it will be assumed that the AE or conmed stopped and the stop date will be imputed, if partial.

#### **Imputation Rules for Partial or Missing Start Dates**

		Stop Date						
		Complete: yyyymmdd		Partial: yyyymm		Partial: yyyy		Missing
Start Date		<1 st Dose	≥1 st Dose	<1 st Dose yyyymm	≥1 st Dose yyyymm	<1 st Dose yyyy	≥1 st Dose yyyy	
Partial: yyyymm	=1 st Dose yyyymm	2	1	2	1	N/A	1	1
	≠ 1 st Dose yyyymm		2		2	2	2	2
Partial: yyyy	=1 st Dose yyyy	3	1	3	1	N/A	1	1
	≠ 1 st Dose yyyy		3		3	3	3	3
Missing		4	1	4	1	4	1	1

1 = Impute the date of first dose

2 = Impute the first of the month

3 = Impute January 1 of the year

4 = Impute January 1 of the stop year

Note: For subjects who were never treated (first dose date is missing), partial start dates will be set to the first day of the partial month.

Note: If the start date imputation leads to a start date that is after the stop date, then do not impute the start date.

## Appendix B. Analytical Windows

The last measurement for the endpoint of interest taken prior to or on the first dose of investigational product in this study, unless stated otherwise will be defined as a baseline visit and the analysis visit name will be “Baseline”. For any visit up to Day 1 pre-dose which is not a baseline visit, the analysis visit will be ‘Pre-Analysis’.

For post-dose assessments on Day 1, post-dose assessments on Day 85 (the day corresponding to week 12 dosing) and assessments at Safety follow-up/EOS visit, the analysis visit will be same as the scheduled visit.

Remaining visits (scheduled or unscheduled) after Day 1 for any assessment will be mapped to the analysis visit based on visit windows defined in the tables below for that assessment. Only visits applicable for that assessment will be considered for analysis.

Data collected through central lab and local lab will both be mapped into analysis visit windows. The local lab data can only be used in analysis when there are no central lab data available in the analysis visit window.

If more than one visit with non-missing data falls within an analysis visit window, the visit closest to the target day will be considered for analysis. If two visits are equidistant from the target day, the latest visit (or time if on the same day) will be considered. If more than one evaluation has same date and time (for chemistry, hematology or pharmacodynamics results), the value with the smallest accession number will be considered.

Analysis visit windows for selected assessments are included in tables below. For remaining assessments, no visit window will be applied. ‘Day 85’ used in study day window calculation in the tables below is the actual study day when Week 12 dose was received. If that dose is missing, then target Day 85 is used for the calculation.

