^g Can be done as a part of the clinical chemistry

^h Pharmacokinetic and lymphocyte subset blood samples should be collected at the exact nominal time point as noted above (see hour postdose column). If unable to collect a blood sample at the specified nominal time point, collect it as close as possible to the nominal time point and record the actual collection time. For samples without exact nominal time point (ie, days 8 to 78), PK samples must be collected prior to administration of investigational product, where appropriate. Pharmacokinetic and lymphocyte subset samples not collected at exact nominal time point will not be considered protocol deviations.

ⁱ DNA will be extracted only in subjects who provide additional consent for pharmacogenetics testing.

^j Investigational product must be administered within \pm 12 hours from the scheduled time point up until week 4. After week 4, investigational product must be administered within \pm 1 day of the scheduled time point. If that window is missed, that dose will not be administered, and the next dose will be administered at the next scheduled dosing date. Subjects will remain at the site for at least 1 hour following the first and second doses of investigational product and for at least 30 minutes following subsequent doses.

^k Subjects who withdraw from investigational product early will complete an early termination visit that includes the week 12 (predose) assessments.

^l To be collected at screening but not required for eligibility unless subject has no documented prior history of antinuclear antibody (ANA) \geq 1:80 or elevated anti-dsDNA.

^m For description of home healthcare services available, see [Section 9.2.3.4](#).

Table 2-2. Schedule of Activities Follow-up

	Follow-up			
	13	14	16	18/SFU/EOS ^a
Study week				
Study day	92	99	113	127
GENERAL AND SAFETY ASSESSMENTS				
Weight				X
Vital signs	X	X	X	X
ECG				X
Adverse events	X	X	X	X ^a
Serious adverse events	X	X	X	X ^a
Disease-related events	X	X	X	X ^a
Concomitant medications review	X	X	X	X ^a
LABORATORY ASSESSMENTS				
Urine pregnancy test			X	X
Anti-dsDNA and C3 and C4 complement				X
Hematology		X	X	X
Chemistry				X
PBMC				X
PHARMACODYNAMIC ASSESSMENTS				
Lymphocyte subsets	X	X	X	X
PHARMACOKINETICS AND ANTIBODIES				
Pharmacokinetic samples	X	X	X	X
Anti-AMG 592 antibody				X
BIOMARKER				
Biomarker development sample				X

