ECG = electrocardiogram; EOS = end of study for individual subject; PBMC = peripheral blood mononuclear cell; SFU = Safety follow-up

^a For subjects who complete the study at week 18, the visit includes all required safety follow up data collection. For subjects who terminate the study early (ie, prior to completing the week 18 visit), the safety follow-up visit 6 weeks (\pm 3 days) after the last dose of investigational product will be a visit to collect adverse events, serious adverse events, disease related events, ECG, **hematology**, and concomitant medications only

3. Introduction

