7.1.1.1.1 Dosage Administration and Schedule

AMG 592 or placebo will be administered by SC injection [REDACTED] starting on Day 1.

The following dose cohorts are planned:

- Cohort 1: [REDACTED] µg [REDACTED] or placebo
- Cohort 2: [REDACTED] µg [REDACTED] or placebo
- Cohort 3: [REDACTED] µg [REDACTED] or placebo
- Cohort 4: [REDACTED] µg [REDACTED] or placebo
- Cohort 5: [REDACTED] µg [REDACTED] or placebo

Investigational product will be administered by SC injection in the abdomen, thigh or upper arm by authorized site personnel. A physician must be available at the time of investigational product administration.

The dose of investigational product must be given within \pm 12 hours of the specified time point up until week 4 (see Schedule of Activities, [Table 2-1](#)). After week 4, doses of investigational product must be given within \pm 1 day of the scheduled time point (see Schedule of Activities, [Table 2-1](#)). If that window is missed, that dose will not be administered, and the next dose will be administered at the next scheduled dosing date.

Subjects will remain at the site for at least 1 hour following the first and second doses of investigational product and for at least 30 minutes following subsequent doses.

The amount of investigational product used in preparation, total volume of preparation, quantity administered, start date, start time, and box number of AMG 592/placebo are to be recorded on each subject's CRF.

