9.1.2 Treatment Period

Visits will occur per the Schedule of Activities ([Table 2-1](#)). On-study visits may be completed within a visit window of \pm 1 day from the scheduled dose date. The date of the first dose of investigational product is defined as day 1. All subsequent doses and study visits will be scheduled based on the day 1 date. Investigational product should be administered after all other study procedures have been completed, except at day 1 and week 12 of the study per the Schedule of Activities ([Table 2-1](#)).

If a subject discontinues investigational product early then he/she should complete an early termination visit as outlined in the Schedule of Activities ([Table 2-1](#) and [Table 2-2](#)).

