### Chemistry

Analysis Visit	Target Day	Start Day	End Day
Week 4, Day 29	29	2	43
Week 8, Day 57	57	44	71
Week 12, Day 85 Pre-Dose	85	72	'Day 85'
Week 18 (SFU), Day 127	127	>'Day 85'	

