### Efficacy assessments (SLEDAI-2K)

Analysis Visit	Target Day	Start Day	End Day
Week 4, Day 29	29	2	43
Week 8, Day 57	57	44	71
Week 12, Day 85 Pre-Dose	85	72	'Day 85'

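### When the Week 12 dose is not given, Appendix B puts a permitted Day 86 visit outside Week 12 in nine of its ten window tables (all but vital signs)

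*SAP*

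**What the plan says.** SAP Appendix B maps visits after Day 1 to analysis visits by study-day windows. Only three kinds of assessment keep their scheduled label: post-dose on Day 1, post-dose on Day 85, and the safety follow-up/end-of-study visit. A Week 12 or early-termination visit without a dose is therefore mapped by window.

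The boundary 'Day 85' in the tables "is the actual study day when Week 12 dose was received". The fallback is: "If that dose is missing, then target Day 85 is used for the calculation". In nine tables the row for the Week 12 pre-dose visit ("Week 12, Day 85 Pre-Dose" in the SLEDAI-2K table) ends at that boundary. In five of them every later day belongs to "Week 18 (SFU), Day 127". If several visits fall in one window, the one closest to the target day is used.

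The protocol sets three conditions that matter here:

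- Section 9.1.2: "On-study visits may be completed within a visit window of" ±1 day.
- Table 2-1, footnote k: "Subjects who withdraw from investigational product early will complete an early termination visit that includes the week 12 (predose) assessments".
- Table 2-2, footnote a: for subjects who leave the study early, the safety follow-up visit "will be a visit to collect adverse events, serious adverse events, disease related events, ECG", hematology and concomitant medications only. It includes no chemistry, serology or antibody sample.

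**The concern.** The boundary follows the dose, not the visit. Two subjects seen on the same compliant day are treated differently according to whether the dose was given. With a dose on Day 86 the boundary moves to 86 and the visit counts as Week 12. Without one the boundary stays at 85 and the visit is a day late for Week 12.

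Two results would be wrong. A SLEDAI-2K or urine protein result can be left out of the by-visit tables, although SAP 9.5.1 and 9.6.3 promise these at all time points. And a chemistry, serology or antibody value taken at the end of treatment can appear as a Week 18 follow-up value. With cohorts of 3 or 5 active subjects, one such case is visible in a dose-group summary.

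**Working it through.** The plan gives no figure to reproduce on this point. The check applies the ten Appendix B tables as written.

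**Inputs**
- Week 12 target day 85 and visit window ±1 day (Protocol 9.1.2): permitted days 85 − 1 = 84 to 85 + 1 = 86.
- Boundary D = day of the Week 12 dose, or 85 if there was none (SAP Appendix B).
- Planned active subjects per cohort: 5 in cohorts 1 to 3, 3 in cohorts 4 and 5 (SAP 3.2).

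**Step 1: where a Day 86 visit lands**

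| Table | Dose on Day 86 (D = 86) | No dose (D = 85) |
|---|---|---|
| SLEDAI-2K | Week 12 | no window |
| Urinalysis | Week 12 | no window |
| Lymphocyte subsets (PD) | Week 12 | Week 13 (86 to 96) |
| Hematology | Week 12 | Week 14 (86 to 106) |
| Chemistry | Week 12 | Week 18 (>85) |
| Weight | Week 12 | Week 18 (>85) |
| Antibody | Week 12 | Week 18 (>85) |
| Anti-dsDNA | Week 12 | Week 18 (>85) |
| C3/C4 | Week 12 | Week 18 (>85) |
| Vital signs | Week 12, Day 85 row | Week 12, Day 86 row |

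With a dose, 10 of 10 tables keep the visit in Week 12. Without one, 1 of 10 does: 2 leave it unmapped, 1 moves it to Week 13, 1 to Week 14 and 5 to Week 18. The vital signs stay in Week 12 but enter the row that the schedule uses for 24 hours after a dose, and no dose was given.

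**Step 2: is a moved value reported under its new label?** Its distance from the new target is 92 − 86 = 6 days (Week 13), 99 − 86 = 13 days (Week 14) or 127 − 86 = 41 days (Week 18). A follow-up visit held on schedule is closer, so the Day 86 value then drops out. It is reported only if that window holds nothing closer. For chemistry, serology and antibody this happens when a subject leaves the study early and so has no such sample at safety follow-up. If the previous scheduled dose was given on time, the value labelled Week 18 was taken 86 − 78 = 8 days after the last weekly dose, or 86 − 71 = 15 days after the last two-weekly dose.

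**Step 3: comparison within the SAP.** The chemistry Week 8 window runs to Day 71, so it accepts a sample 71 − 57 = 14 days after target. The Week 12 window without a dose accepts 85 − 85 = 0 days after target. For PD, SAP 9.7.1.2 excludes early-termination data only beyond 9 days (weekly) or 16 days (two-weekly) after the last dose. From Days 78 and 71, both limits reach 78 + 9 = 71 + 16 = Day 87. That limit would admit a Day 86 sample which Appendix B places in Week 13.

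**Step 4: weight of one subject.** 1/5 = 20% of a 5-active cohort; 1/3 = 33% of a 3-active cohort.

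**Step 5: effect of setting D = 86.** All ten tables return a Day 86 visit to Week 12, and later windows stay in order: PD Week 13 becomes 87 to 96, hematology Week 14 becomes 87 to 106, and vital signs Week 13 becomes 90 to 96.

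**The case against.** The case for leaving this alone is that it is a narrow edge case in descriptive tables. Much of that stands. Adverse events do not use these windows. Laboratory maxima, minima and worst-grade shifts are not tied to one visit label, and Protocol 10.3.2.4.2 counts antibodies at any time. SLEDAI-2K, serology and PD are exploratory, and SAP 2.2 plans no formal hypothesis. For PD, the skipped-dose exclusion in SAP 9.7.1.2 may remove the sample whatever its window; its wording is unclear for a visit that was meant to be pre-dose.

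A reader might infer more than the documents support:

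- *That every Week 12 window fails.* Vital signs have Week 12 rows through Day 88.
- *That the values are routinely reported as Week 13, 14 or 18.* The closest-visit rule prevents this when the later visit took place on time. Subjects who stop drug may stay on the schedule (Protocol 8.1).
- *That a missed dosing window causes the problem.* Protocol 7.1.1.1.1 says of a late dose: "If that window is missed, that dose will not be administered, and the next dose will be administered at the next scheduled dosing date". After week 4 that window is ±1 day, the same as the visit window. A compliant Day 86 visit is therefore still inside it, and missing it on the late side means Day 87 or later. What remains is a dose withheld or treatment stopped.
- *That one in three undosed visits is affected.* This assumes Days 84, 85 and 86 are equally likely, for which the documents give no basis.
- *That those affected had tolerability problems.* The documents do not say so, and SAP 9.6.8 expects some doses to be missed because of COVID-19.

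None of this removes the inconsistency for a compliant Day 86 visit.

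**Conclusion.** Wrong as written, minor severity. For a subject with no Week 12 dose whose Week 12 or early-termination visit was on Day 86, nine of ten tables take the visit out of Week 12. Two give it no analysis visit. Seven move it to a later window, where it is reported only if nothing closer to target is there. The effect is confined to by-visit descriptive summaries. The documents do not say how many of the approximately 29 planned subjects would meet these conditions, and it may be none. The 20% and 33% figures are the weight of one subject at the planned cohort sizes, not an expected loss.

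**What to change.** In Appendix B, replace the fallback sentence with one to this effect: where no Week 12 dose was given, use the actual study day of the scheduled Week 12 or early-termination visit if that visit took place on Day 86, the end of the protocol's ±1-day visit window; in every other case use Day 85.

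The cap at Day 86 is needed. Without it, an early-termination visit on Day 100 would make the PD Week 13 window run from 101 to 96, and PD Week 12 (83 to 100) would overlap Week 14 (97 to 106). A visit on Day 87 or later is outside the protocol window and would be mapped as it is now.

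Leave the Week 18 windows starting after 'Day 85'. Starting them at Day 107, just past the midpoint (85 + 127)/2 = 106, may look tidier. But if the Week 12 dose is given on Day 85, unscheduled chemistry, serology, antibody and weight results from Days 86 to 106 would then have no window, while SAP 9.6.3 intends to use unscheduled laboratory assessments where possible.

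The cost is one SAP sentence and a small change to the window program. No new data are needed.

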### Vital Sign

Analysis Visit	Target Day	Start Day	End Day
Week 1, Day 2	2	2	2
Week 1, Day 3	3	3	3
Week 1, Day 4	4	4	6
Week 1, Day 8	8	7	9
Week 1, Day 11	11	10	12
Week 2, Day 15	15	13	19

Week 3, Day 22	22	20	26
Week 4, Day 29	29	27	33
Week 5, Day 36	36	34	40
Week 6, Day 43	43	41	47
Week 7, Day 50	50	48	54
Week 8, Day 57	57	55	61
Week 9, Day 64	64	62	68
Week 10, Day 71	71	69	75
Week 11, Day 78	78	76	'Day 85' - 1
Week 12, Day 85	85	'Day 85'	
Week 12, Day 86	86	'Day 85' + 1	'Day 85' + 1
Week 12, Day 87	87	'Day 85' + 2	'Day 85' + 2
Week 12, Day 88	88	'Day 85' + 3	'Day 85' + 3
Week 13, Day 92	92	'Day 85' + 4	96
Week 14, Day 99	99	97	106
Week 16, Day 113	113	107	120
Week 18 (SFU), Day 127	127	>120	

